7.1.1 Inceptiv Implantable Neurostimulator

The Inceptiv implantable neurostimulator is a rechargeable, multiprogrammable device that delivers electrical stimulation through one or more leads. The stimulation settings are stored in programs to target specific effects or areas. A program is a specific combination of pulse width, rate, and intensity settings acting on a specific electrode combination.

Medtronic has developed an optional closed-loop feature to improve a patient's experience with SCS therapy, specifically targeting overstimulation. The closed-loop algorithm is able to sense the body's physiological ECAP response, and automatically react, based on the spinal cord's response to stimulation.

7.1.2 Vectris SureScan MRI 1x8 Compact

The percutaneous leads are connected to the implantable neurostimulator. Each lead has electrodes on the distal end; the proximal (connector) end fits into an 8-conductor connector. A stylet can be inserted into the proximal end of the lead to aid in positioning the lead.

7.1.3 Specify SureScan MRI 5-6-5

The surgical leads are connected to the implantable neurostimulator. The lead has 16 electrodes on the distal end; two proximal ends fit into 8-conductor connectors. Up to three low-back and/or leg subjects may be implanted with surgical leads.

7.1.4 Wireless External Neurostimulator

The Wireless External Neurostimulator is part of a neurostimulations system used for intraoperative testing during lead placement and for trial stimulation outside of the operating room.

7.1.5 Vectris MRI 1x8 Compact

The trial leads are connected to the wireless external neurostimulator. Each lead has electrodes on the distal end; the proximal (connector) end fits into an 8-conductor connector. A stylet can be inserted into the proximal end of the lead to aid in positioning the lead. The trial leads are contraindicated for long-term implantation and must be removed within ten days of implant.

7.1.6 Boot

The boot is an external single-use-only accessory that is used with the wireless external neurostimulator to adhere the wireless external neurostimulator externally to the patient's body during the duration of the trial period.

7.1.7 Clinician Tablet

The Clinician Tablet, a Samsung tablet with Android operating system, is a nonsterile, commercially available, off-the-shelf, non-medical device. The Clinician Programmer Application and the Stimulation Clinician Trialing Programmer Application operate on this platform.

7.1.8 Clinician Programmer Application

The Clinician Programmer Application (CPA) is a mobile medical application designed for use by clinicians to interrogate and program medical devices. It is designed to configure and manage SCS therapy parameters by the clinicians for Inceptiv. The CPA will run on the Clinician Tablet which is a non-medical off-the-shelf tablet. Additionally, with the CPA, the Communication Manager Application (non-medical), and Patient Data Services Application (non-medical) will be utilized. The Communicator will serve as a telemetry bridge between the Clinician Tablet and Inceptiv.

7.1.9 Patient Programming Application

The Patient Programming Application (PPA) will operate on the Patient Handset and be used by patients (and/or their caregivers) to manage their therapy provided by Inceptiv.

7.1.10 Stimulation Trialing Clinician Programmer Application

The Stimulation Trialing Clinician Programmer Application allows clinicians to program wireless external neurostimulators during trialing by adjusting the rate, pulse width and amplitude of the therapy provided to the patient.

7.1.11 Patient Programmer Trialing Application

The Patient Programmer Trial Application operates on the Patient Handset and will be used by patients to manage their therapy during a trial. The Patient Programmer Trial Application allows the patient to make therapy programming adjustments to the wireless external neurostimulator. The Patient Handset has a user interface display and Bluetooth interface to the wireless external neurostimulator. The Patient Handset is constrained to a Commercial-Off-The-Shelf Android mobile phone.

7.1.12 Patient Telemetry Communicator

The Patient Handset works in conjunction with the Patient Telemetry Communicator to provide the programming/controlling capabilities to patients. Specifically, a communication bridge is formed from the Patient Handset, using Bluetooth Low Energy (BLE) signals, through the Telemetry Module to Inceptiv, using Tel-M and Tel-Np communication protocols, respectively.

7.1.13 Communicator

The Communicator is considered part of the clinician programmer system. The Communicator was originally developed for use across Medtronic Neuromodulation therapies. It is a non-sterile, battery-operated, external device designed to create a communication bridge between the Mobile Platform and Inceptiv.

7.1.14 Connector Plug

The Connector Plug is a sterile device that is intended to be inserted into the unused connector of Inceptiv.

7.1.15 Recharger Subsystem

The Recharger Subsystem is a kit that is designed to support the patient in their recharge needs.

The fixation belt is intended to support the Recharger during a patient's recharge session; however, the patient may choose to hold the recharger manually or via other means. The Recharger Belt is not required for the recharger to achieve its intended purpose, which is to recharge the Inceptiv.

- Recharger and application
- Fixation Belt
- CD9000 Charging Dock + Power Adapter
- USB cord and AC adaptor (commercial, off-the-shelf non-medical devices)
- System carrying case (non-medical device)

7.2 Manufacturer

There are several manufacturers of the study products, see Table 3.

7.3 Packaging

The Inceptiv device and accompanying investigational products will be labeled “Exclusively for clinical investigations”.

7.4 Intended Population

The study device is indicated for SCS as an aid in the management of patients with chronic, intractable pain of the trunk and/or limbs. Study eligibility criteria must be met to participate, see Section 9.

7.5 Equipment

The following equipment must be available at each study site to support study activities:

- Fluoroscopy/x-ray with electronic output

This equipment will be maintained/calibrated according to the study site’s standard protocol. Maintenance and calibration reports may be monitored periodically by the monitor.

7.6 Product Use

Instructions for Inceptiv and accompanying products will be provided in the Investigator’s Brochure. Refer to existing manuals for market released product.

7.7 Product Training Materials

Investigators will be chosen to participate in this study based on being qualified by training, education, and relevant experience appropriate for the use of spinal cord simulators. Study specific training will be conducted pertinent to the involvement of personnel conducting study activities and Investigator responsibilities. All Investigators and site personnel will be trained on the Clinical Investigation Plan (CIP) prior to their participation on the study.

7.8 Product Receipt and Tracking

Sites with these clinically labeled products will track disposition upon receipt or return of the products, as well as upon implant or explant of the product. Tracking includes dates and quantities received, used, explanted and returned. Lot/serial numbers and expiration dates will be documented and used for traceability. All of these elements will be entered on an electronic Case Report Form (eCRF).

7.9 Product Storage

Investigational product, once received at the study site, must be stored in a secure location at the study site. It is the responsibility of the investigator to correctly handle, store, and track the investigational products maintained at the study site. Investigational products will be used only in the clinical study according to the CIP.

7.10 Product Return

All explanted devices (devices or permanent leads) should be returned to Medtronic for analysis when permissible by local laws and regulations. If the products are explanted but not returned, a justification will be reported on the appropriate case report forms or disposition logs. To receive a Returned Product Mailer Kit, please contact your local Medtronic field personnel.

7.11 Product Accountability

Product delivery

Market-released products:

Commercially available product supply will be managed in a manner consistent with other market-released products.

Investigational products:

Investigational products will be distributed to a study site only when Medtronic has received all required documentation and has notified the study site of study site activation. Distribution of investigational product to study sites during the study will be managed by Medtronic and can only be ordered by Medtronic personnel.

Product receipt and tracking

Market-released products:

There are no additional local requirements related to the market-released product beyond what is collected by Medtronic on the eCRF, this is the Investigator's responsibility and should be recorded in the subject's medical records, but will not be collected by Medtronic.

Investigational products:

The study site is responsible for maintaining tracking of the investigational products during the study. The tracking method might vary, but could use either electronic or paper accountability logs provided by Medtronic. The accountability logs must be maintained at each study site and updated when the investigational product is received, opened, implanted, explanted, disposed of or returned to Medtronic. In addition to tracking the date of events, the accountability log tracks product information including, but not limited to, date, model/serial number, and expiration date for the received product, subject ID of the implanted subject, reason(s) for and method of destruction/disposal for explanted components not returned to Medtronic (if applicable), and name of the person responsible for return or destruction/disposal (if applicable).

Medtronic will perform periodic reconciliation of the investigational product to ensure traceability.

8. Study Site Requirements

8.1 Investigator/Investigation Site Selection

The role of the Principal Investigator is to implement and manage the day-to-day conduct of the clinical investigation as well as ensure data integrity and the rights, safety and well-being of the subjects involved in the clinical investigation.

The principal investigator/site shall:

- Investigator/site is qualified by training, education, and relevant experience appropriate to the use of the product and associated procedures (Spinal Cord Stimulation)
- Investigator/site expects to have adequate time and resources to conduct the study throughout the duration of the study (up to 24-months of follow up activities)

- Investigator/site has access to an adequate number of eligible subjects (enroll at least 1 patient per month)
- Investigator/site has the ability to comply with applicable Ethics Committee (EC) and regulatory requirements
- Investigator is not debarred, disqualified, or working under sanctions
- Site has adequate facilities for study subjects to complete study assessments
- Has ability to perform fluoroscopy/x-ray with electronic output

8.2 Study Site Activation

During the activation process (prior to subject enrollment), Medtronic will train study site personnel on the Clinical Investigation Plan, relevant standards and regulations, informed consent (IC), and data collection and reporting tools. If new members join the study site team, they will receive training on the applicable study requirements relevant to their role before contributing to the study.

Prior to performing study related activities, all regulatory requirements shall be fulfilled, including, but not limited to the following:

- Ethics Committee (EC) approval (and voting list when a site team member is an EC member) of the current version of the CIP and IC.
- EC approval or acknowledgement of subject-facing materials and subject recruitment/advertising (if applicable)
- Regulatory Authority (RA) approval or notification, if applicable
- Fully executed Clinical Trial Agreement (CTA)
- Financial disclosure
- CV of investigators and key members of the investigation study site team (as required). The signature on the CV must be dated within 3 years prior to the date of activation of the study site.
- Documentation of delegated tasks
- Sponsor technical support list
- Documentation of study training (a separate training document will overview topics and include details on the format of delivery including the CIP, informed consent process, data collection tools, regulations and the devices)
- Additional requirements imposed by local regulations, the EC and RA shall be followed, if appropriate.

In addition, all participating study site staff must be trained on the current version of the CIP as well as on the applicable study requirements depending on their role and must be delegated by the Principal Investigator to perform study related activities.

Medtronic will provide each study site with documentation of study site/Investigator readiness; this letter must be received prior to performing study related activities.

8.3 Role of the Sponsor Representatives

In addition to performing monitoring and auditing activities, sponsor representatives may provide support at the study site as required for the study under supervision of the Principal Investigator, including:

- Provide study training relevant and pertinent to the involvement of personnel conducting study activities and investigator responsibilities
- Technical support under the supervision of a study Investigator, but no data entry, shall be performed by Medtronic personnel or their representatives at study sites

In addition, for this study, sponsor representatives may be authorized by the Principal Investigator to perform the following significant study related duties:

- Support study Investigators in performing the study trial and implant procedures including device programming, interrogations and transmission of study data
- Support data collection during the trial and implant procedure and device testing
- Support data collection during the study visits
- Contact subjects to troubleshoot their device settings
- Due to extenuating circumstances, trained Medtronic personnel may remotely assist with in-person technical support via live video streaming from a secure and compliant service. The live stream will not be recorded and will be accessible only to authorized sponsor technical support representative through a secure service during the visits

Any data collection completed by Medtronic personnel will be clearly identified as such.

9. Selection of Subjects

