10.15 Randomization and In-Clinic Testing

In-Clinic Testing will occur within 30 days ± 5 days from Device Activation and again at the 3- and 12-Month Visits. A clear and measurable ECAP must be present in order to be randomized during in-clinic testing. Subjects will be randomized to either Neuro Sense On followed by Neuro Sense Off in-clinic testing, or Neuro Sense Off followed by Neuro Sense On testing. The subject will be blinded to the settings tested.

The following information is required to be collected during the in-clinic testing visit:

- [REDACTED]
- Randomization assignment
- Subject rating of stimulation sensation with Likert scale

[REDACTED]

[REDACTED]

- █ [REDACTED]
- █ [REDACTED]
- Collect data files via the clinician programmer tablet and securely send to Medtronic
- Pain medications
- AEs/device deficiencies

[REDACTED]

[REDACTED]

[REDACTED]

█ [REDACTED]

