10.15.3 Blinding

The in-clinic testing phase of the study will be single blinded to reduce bias. The subject will not have knowledge of the therapy assigned during the in-clinic testing phases of the study. It is essential that study sites take special precaution to maintain the blind during the in-clinic testing. It is recommended that records and printouts that disclose the subject's randomization assignment be kept in the medical record and/or study file in envelopes, so as to protect the blinded status. Other options to maintain the blinding may be applied per investigational study site research procedure.

Medtronic personnel will be unblinded to randomization assignments.

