10.21 Assessment of Efficacy

10.21.1 Overstimulation Sensation

All assessments will be documented in a paper format by the subject and transferred to the appropriate visit eCRF by authorized site personnel. For every overstimulation sensation brought about by protocol-prescribed activities, subjects will rate the intensity of the sensation in the following 5-point Likert scale:

- No overstimulation sensation (code=0)
- Weak overstimulation sensation (code=1)
- Moderate overstimulation sensation (code=2)
- Strong overstimulation sensation (code=3)
- Very strong overstimulation sensation (code=4)

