14.9 Minimization of Bias

Selection of subjects, treatment of subjects, and evaluation of study data are potential sources of bias. Methods incorporated in the study design to minimize potential bias include (but are not limited to):

- Subjects' in-clinic testing sequences are randomized with stratification at each site. This is to ensure subjects get equal opportunities to start with either Neuro Sense On or Off testing.
- Subjects are blinded to the Neuro Sense On or Neuro Sense Off testing settings. This is to ensure that the knowledge of testing settings is not going to influence the subjects' assessment of overstimulation sensation.
- Missing data are a potential source of bias when analyzing study data. A rigorous study design and execution will help prevent the incidence of missing data from occurring. All efforts will be made to ensure patient visits are completed with limited attrition to ensure interpretability of study results.
- To reduce the possibility of atypical results from a site overly influencing the combined results, the maximum number of subjects to be enrolled at a single study site is limited to 18 and cannot be increased without prior sponsor approval.
- A statistical analysis plan will be developed prior to analyzing data which will document all prespecified analyses and analysis methods.
- All study investigators will be trained on and required to follow the CIP.
- All study investigators and Medtronic personnel will be trained on their respective aspects of the study using standardized training materials.
- All sites will use the same version of the CIP and standardized case report forms.
- Monitoring will be conducted to verify adherence to the CIP.

In summary, potential sources of bias that may be encountered in this study have been considered and minimized by careful study design.

15. Ethics

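### Unblinded sponsor personnel may support data collection at the in-clinic testing visit, and the readable text makes no exception for the self-rated primary endpoint, leaving it open to cueing

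*Protocol*

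**What the plan says.** **Sponsor role.** Protocol 8.3 lists duties that the Principal Investigator may authorize sponsor representatives to perform. Two concern data collection: "Support data collection during the trial and implant procedure and device testing", and, as a separate item, "Support data collection during the study visits". The same section bars sponsor personnel from data entry, places their technical support under investigator supervision, and requires any data collection they complete to be identified as theirs.

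**Blinding.** Protocol 10.15.3 states: "The in-clinic testing phase of the study will be single blinded to reduce bias". It also states: "Medtronic personnel will be unblinded to randomization assignments". Sites are told to take special care to keep the blind. The concrete measure named is keeping records that show the assignment in envelopes. Section 10.15.4 asks for reasonable efforts to prevent unblinding of the subject.

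**The rating.** Protocol 10.15 lists among the data required at the in-clinic testing visit: "Subject rating of stimulation sensation with Likert scale". Under 10.21.1, "All assessments will be documented in a paper format by the subject and transferred to the appropriate visit eCRF by authorized site personnel".

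**The endpoint.** Protocol 14.4.1.2 and SAP 7.9.1.2 average each subject's ratings within each period. A subject is a success if the On (closed-loop) average is lower than the Off (open-loop) average. No minimum difference is set.

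**Bias control.** Protocol 14.9 includes the statement "Subjects are blinded to the Neuro Sense On or Neuro Sense Off testing settings". It also lists sequence randomization stratified by site, training of investigators and sponsor personnel, standardized case report forms and monitoring. It does not address unblinded personnel helping to collect the ratings.

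**The concern.** The primary endpoint rests entirely on what the subject says about a sensation, given after each of 3 to 5 activities (Synopsis). Blinding of the subject is the main protection for that answer. If someone who knows the setting, and whose employer has an interest in the result, asks for the rating, stands by while it is given or handles the form, the answer can be influenced without any intent to do so. Tone, timing or a repeated question is enough.

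The endpoint rule makes small influences count. A one-point change on one activity separates a tie, which is a failure, from a success. The objective is decided on 28 subjects against a fixed 50% goal, so a modest systematic shift would act directly on the error rate of the test.

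**Working it through.** **1. Does the permission reach the primary ratings?**
- Knowledge of the setting: 10.15.3 leaves sponsor personnel unblinded, without qualification.
- Access: the device-testing item in 8.3 names testing together with the trial and implant procedure, so it could mean only testing at those procedures. The study-visits item is not limited in that way and covers the Randomization and In-Clinic Testing visit. It is the firmer support.
- Content: 10.15 lists the Likert rating among the data required at that visit, alongside device files and medications. Section 8.3 does not separate the rating from the rest.

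Read together, a person who knows the setting may, if authorized, support collection of the ratings.

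**2. Do the existing safeguards close the gap?**
- Subject records on paper (10.21.1): controls who writes, not who asks, prompts or looks on.
- No sponsor data entry (8.3): controls transcription, which comes after any cueing.
- Sponsor-collected data identified (8.3): gives traceability after the event.
- Authorization and supervision by the investigator (8.3): general oversight, with no rule specific to the rating.
- Care to preserve the blind (10.15.3, 10.15.4): general wording, and envelopes protect records rather than conversation.

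Each reduces the risk. None that is readable prevents prompting.

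**3. The plan's own figure.** Inputs from the Synopsis and 14.4.1.5: n = 28, null proportion 0.50, alternative 0.80, exact binomial test, one-sided alpha 0.025. The smallest r with P(X ≥ r | 28, 0.50) < 0.025 is needed.
- P(X ≥ 19 | 28, 0.50) = 0.0436, too large.
- P(X ≥ 20 | 28, 0.50) = 0.0178, so success needs at least 20 of 28.
- Power: P(X ≥ 20 | 28, 0.80) = 0.910.

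The stated power of more than 90% with 28 subjects is reproduced.

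**4. How small a nudge matters?** With k activities rated in each period, one point on one rating moves that period's average by 1/k: 1/3 = 0.33 for three activities, 1/5 = 0.20 for five. Equal averages are a failure. One point lower under On makes the same subject a success. If the On total is one point higher than the Off total, one point only produces a tie, and two points are needed for success.

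**5. Illustration of the effect on the test.** The documents give no size for cueing, so the values of p below are assumptions. Formula: P(X ≥ 20 | 28, p), where p is the chance that a subject counts as having a reduction when the feature has no effect.

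| p | P(at least 20 of 28) |
|---|---|
| 0.50 | 0.0178 |
| 0.52 | 0.0294 |
| 0.55 | 0.0578 |
| 0.60 | 0.1485 |

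The value at 0.60 is 0.14848 before rounding, that is 14.8%.

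**6. Effect of ties.** With no effect and no cueing, increases and reductions are equally likely, so the unbiased p is (1 − tie rate)/2. If 10% of subjects tied (an assumption), p = 0.45 and the chance of success is 0.0043. Adding 5 or 10 points then gives p = 0.50 or 0.55, with 0.0178 or 0.0578. For a given shift, the figures in step 5 are therefore upper values.

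**The case against.** The strongest reply is that the plan does what it says. A single blind covers the subject, and an unblinded operator is consistent with it. A reader might infer that the permission breaks or undermines the single blind. The documents do not support that: nothing in them shows the setting reaching the subject. What stands is a risk of cueing or inadvertent unblinding.

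A reader might also infer that nothing in the plan prevents this. That cannot be known. Section 10.15.1, on set-up and testing, appears in the contents but its text is redacted, and it is where conduct of the ratings would be expected. The point is limited to the readable text. Even so, the permission in 8.3 carries no exception.

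Two further inferences go too far. Section 14.9 does not rely on subject blinding alone. And the programming support in 8.3 is tied to the trial and implant procedures, so the readable text does not establish that sponsor personnel program the device at in-clinic testing. The point needs only their knowledge of the assignment, which 10.15.3 gives.

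Finally, the error rates rest on an assumed size of cueing, and ties lower the starting rate. Both objections stand, so the figures show sensitivity and are not an estimate of the trial's false-positive rate. This is also a feasibility study, and there is no contradiction in the text or error in the statistics.

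**Conclusion.** The concern holds in a limited form. Sections 8.3 and 10.15.3 together permit unblinded sponsor personnel to support data collection where the self-rated primary endpoint is taken, and the readable text does not exempt the ratings. This is a stated permission that exposes the endpoint, not merely a missing detail. The existing safeguards reduce the exposure but do not prevent prompting.

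The size is unknown. On assumed shifts of 5 or 10 points from a 50% base, the chance of a false success goes from 1.8% to 5.8% or 14.8%. A shift of 2 points gives 2.9%, already above the planned 2.5%. With ties these are upper values: if 10% tie, 5 points gives 1.8% and 10 points gives 5.8%. The sample size, the alpha and the test are unaffected. The change is worth making because it is cheap and protects the one hypothesis test in the study.

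**What to change.** - **Protocol 8.3:** exclude the in-clinic overstimulation ratings from the data collection that sponsor personnel may support.
- **Protocol 10.15.3:** state that sponsor personnel do not ask for, prompt, view before completion or record a rating. The subject marks the paper form unaided after each activity and hands it to site personnel, who already transfer it under 10.21.1.

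If the redacted 10.15.1 already contains such a rule, a cross-reference from 8.3 and 10.15.3 is enough. The same wording would cover the repeat testing at the 3- and 12-Month Visits.

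The cost is an amendment to the wording and site training. No extra staff are needed, because the subject and site personnel already hold these tasks. Barring every person who knows the setting would go further, but could require a second person at some sites, so it is not proposed. The downside is slightly less flexibility for sponsor field staff on the testing day.
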